## **8.0 PHARMACEUTICAL INFORMATION**

### **8.1 Dexrazoxane (Zinecard)**

In the event of a national shortage of dexrazoxane, 72-hour infusional doxorubicin can be used in place of dexrazoxane and bolus doxorubicin.

#### **8.1.1 Dexrazoxane Description**

Dexrazoxane is a cardioprotective agent for use in conjunction with doxorubicin. Chemically, dexrazoxane is (S)-4,4'-(1-methyl-1,2-ethanediyl)bis-2,6-piperazinedione. The molecular formula is C11H16N4O4, and its molecular weight is 268.28.

#### **8.1.2 Clinical Pharmacology**

The mechanism by which dextrazoxane exerts its cytoprotective activity is not fully understood. Dextrazoxane is a cyclic derivative of EDTA that penetrates cell membranes. Results of laboratory studies suggest that dextrazoxane is converted intracellularly to a ring-opened chelating agent that interferes with iron-mediated free radical generation thought to be responsible, in part, for anthracycline-induced cardiomyopathy.

### **8.1.3 Pharmacokinetics and Drug Metabolism**

The pharmacokinetics of dextrazoxane can be adequately described by a two-compartment open model with first-order elimination. The mean peak plasma concentration of dextrazoxane was 36.5  $\mu\text{g}/\text{mL}$  at 15 minutes after intravenous administration of 500  $\text{mg}/\text{m}^2$  of dextrazoxane.

Qualitative metabolism studies have confirmed the presence of unchanged drug, a diacid-diamide cleavage product, and two monoacid-monoamide ring products in the urine of animals and man.

### **8.1.4 Supplier(s)**

Dextrazoxane is available commercially and will be billed as standard of care.

### **8.1.5 Dosage Form and Preparation**

Dextrazoxane is available as 250 mg or 500 mg single dose vials as sterile, pyrogen-free lyophilizates.

Reconstitute dextrazoxane with Sterile Water for Injection, USP. Reconstitute with 25 mL for a dextrazoxane 250 mg vial and 50 mL for a dextrazoxane 500 mg vial to give a concentration of 10  $\text{mg}/\text{mL}$ . Dilute the reconstituted solution further with Lactated Ringer's Injection, USP to a concentration of 1.3 to 3.0  $\text{mg}/\text{mL}$  in intravenous infusion bags for intravenous infusion.

Parenteral drug products should be inspected visually for particulate matter and discoloration prior to administration, whenever solution and container permit. Solutions containing a precipitate should be discarded.

### **8.1.6 Storage and Stability**

Reconstituted dextrazoxane for injection, when transferred to an empty infusion bag, is stable for 6 hours from the time of reconstitution when stored at controlled room temperature, 20° to 25°C (68° to 77°F) or under refrigeration, 2° to 8°C (36° to 46°F). **DISCARD UNUSED SOLUTIONS.** The reconstituted dextrazoxane for injection solution may be diluted with either 0.9% Sodium Chloride Injection, USP or 5% Dextrose Injection, USP to a concentration range of 1.3 to 5  $\text{mg}/\text{mL}$  in

intravenous infusion bags. The resultant solutions are stable for 6 hours when stored at controlled room temperature, 20° to 25°C (68° to 77°F) or under refrigeration, 2° to 8°C (36° to 46°F). DISCARD UNUSED SOLUTIONS.

### **8.1.7 Administration**

Administer the final diluted solution of dexrazoxane by intravenous infusion over 15 minutes before the administration of doxorubicin. DO NOT ADMINISTER VIA AN INTRAVENOUS PUSH. Administer doxorubicin within 30 minutes after the completion of dexrazoxane infusion.

### **8.1.8 Special Handling Instructions**

Use caution when handling and preparing the reconstituted solution. The use of gloves is recommended. If dexrazoxane powder or solutions contact the skin or mucosae, wash exposed area immediately and thoroughly with soap and water. Follow special handling and disposal procedures.

## **9.0 CORRELATIVE STUDIES**

### **9.1 Evaluation of Cardiac Function with Echocardiogram**

Patients receiving dexrazoxane will undergo cardiac evaluation with echocardiograms every six weeks to evaluate for cardiac function.

Left ventricular ejection fraction (LVEF) will be evaluated by 2D echocardiogram by modified Simpson's biplane method will be provided to investigators within two days of the evaluation. Treatment decisions regarding cardiac safety will be determined by a decrease in LVEF by 2D echocardiogram (modified Simpson's biplane method) based on the clinical reading.

In addition, cardiac function will be evaluated using these images and interpreted by offline research echocardiographic laboratory and this interpretation will not be made available to the treating physicians, however the PI will have access for non-clinical purposes. Left ventricular systolic function will also be evaluated by 3D echocardiogram when technically possible.

Left ventricular diastolic function will be evaluated by mitral inflow pulsed wave Doppler to evaluate the mitral E velocity, mitral E deceleration time and mitral A velocity. Tissue Doppler imaging of the mitral annulus will also be evaluated. Load Independent Index of Filling (LIIF) will be measured. It should be noted that this has never been done outside a research laboratory. This measurement in this part of the protocol is experimental.

Right ventricular systolic function will be measured and cardiac valves will be evaluated. The additional cardiac measurements, specifically 3D echocardiogram calculated ejection

fraction, left ventricular strain, will be used to evaluate for an early or more precise measurement of cardiac dysfunction.

Additional controls for these analyses will be collected from the sarcoma banking study (HRPO #201203042) under a waiver of consent. Identifiers will be collected in order to perform the chart review. The chart review will be performed to assess for cardiac function and symptomatic heart failure.

## **9.2 Measurement of High Sensitivity Troponin-I (hscTnI) and Galectin-3**

Blood will be drawn with pre-clinic blood work and 4 hours after doxorubicin exposure with each cycle of chemotherapy (collected at baseline and Day 1 of every cycle for control group up to Cycle 6). Ten mL of whole blood should be drawn into an EDTA tube. Blood samples will be sent to the lab of [name] in pathology to be run in large batches.

## **9.3 Measurement of Brain-type Natriuretic Peptide (BNP)**

Patients receiving dexrazoxane will have blood drawn to measure BNP. Blood will be drawn in an EDTA (lavender top) tube as a baseline measurement before Cycle 1 and then after a cumulative dose of 300mg/m^2 of doxorubicin. In patients continuing to receive doxorubicin after a cumulative dose of 300mg/m^2, a BNP will be measured every 6 weeks. A total of 2mL of blood needs to be collected in each EDTA tube or the lab may be added onto a basic metabolic panel or complete metabolic panel if done prior to chemotherapy. BNPs will be performed as a clinical test to evaluate early appearance of cardiac toxicity and clinically relevant LV systolic deterioration. An increase of BNP above normal or baseline will trigger additional evaluation of cardiac function (another echocardiogram) and possibly evaluation by cardiology per treating oncologist's discretion.

## **9.4 Heart Rate Variability**

All patients receiving dexrazoxane will be wear a small, 3-channel Holter monitor (MyPatch,® DMS Holter, Stateside, CA) to record their continuous 24 hour electrocardiogram in order to examine their cardiac rhythm and measure heart rate variability (HRV). The patch recorder will be placed at the time of the baseline, 6 week and subsequent clinical echocardiograms by a cardiac tech in the north CDL. Patients will be instructed to remove the myPatch recorder after 24 hours. It should then be placed in an envelope provided by the study and FedEx pick-up. Once the HRV devices have been returned to the Washington University Cardiology Department, recordings will be scanned by the research technician at the HRV Lab and then overread for scanning accuracy by [name], Director of the HRV Lab. If any clinical abnormalities are seen on the Holter recording, [name] will be notified and a copy of the Holter report provided to him.

## 10.0 STUDY CALENDAR

### 10.1 DEXRAZOXANE ARM

Baseline/screening procedures may take place up to 14 days prior to the start of treatment, except consent and scans (including the echocardiogram and Holter monitor), which may take place up to 28 days prior to the start of treatment.

	Baseline / Screening	Day 1 of Each Cycle	Day 1 of Each Odd-Numbered Cycle 	End of Each Even-Numbered Cycle	EOT	F/U 
Informed consent	X					
H&P, ECOG PS	X				X	X
CBC	X					
CMP	X					
β-hCG 	X					
2D and 3D echocardiogram	X		X 			
CT C/A/P	X			X	X	
Dexrazoxane 		X				
Blood for hscTnI and galectin-3		X 				
Blood for BNP 	X		After cumulative dose of 300 mg/m  of doxorubicin, and then every 6 weeks thereafter			
24-hour Holter monitor	X		X			
AE assessment	X				X	

1. Women of childbearing potential only
2. Can be drawn with a BMP or CMP if being drawn for routine pre-doxorubicin labs
3. Every 3 months for up to 5 years; Patients who are removed for reasons other than progression will be followed until standard of care imaging shows progression per RECIST 1.1.
4. No more than 30 minutes before SOC doxorubicin
5. With SOC pre-treatment bloodwork and 4 hours post-doxorubicin
6. Except Cycle 1
7. -3 day window to allow for the echo to be read prior to the start of the next cycle

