## **5.0 TREATMENT PLAN**

### **5.1 Agent Administration**

Dexrazoxane will be given intravenously on an outpatient basis over 15 minutes on each day that doxorubicin is given. Dexrazoxane should be given no more than 30 minutes prior to administration of doxorubicin, which is typically given on Day 1 of a 21-day cycle. Dosing is a 10:1 ratio of dexrazoxane to doxorubicin; doxorubicin will be started at 75 mg/m^2, so dexrazoxane dosing would be 750 mg/m^2. Doxorubicin is being given as routine care; the administration is not dictated per protocol. Patients who are enrolled in the control group will receive institutional standard of care therapy.

In the event of a national shortage of dexrazoxane, 72-hour infusional doxorubicin can be used instead of dexrazoxane and bolus doxorubicin.

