## **5.4 Duration of Therapy**

If at any time the constraints of this protocol are considered to be detrimental to the patient's health and/or the patient no longer wishes to continue protocol therapy, the protocol therapy should be discontinued and the reason(s) for discontinuation documented in the case report forms.

In the absence of treatment delays due to adverse events, treatment with dexrazoxane may continue as long as treatment with doxorubicin continues or until one of the following criteria applies:

- Documented and confirmed disease progression
- Death
- Adverse event(s) that, in the judgment of the investigator, may cause severe or permanent harm or which rule out continuation of study drug
- General or specific changes in the patient's condition render the patient unacceptable for further treatment in the judgment of the investigator
- Suspected pregnancy
- Serious non-compliance with the study protocol
- Lost to follow-up
- Patient withdraws consent
- Investigator removes the patient from study
- The Siteman Cancer Center decides to close the study

Patients who prematurely discontinue treatment for any reason will be followed as indicated in the study calendar.

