## 11.0 DATA SUBMISSION SCHEDULE

Case report forms with appropriate source documentation will be completed according to the schedule listed in this section.

Case Report Form	Submission Schedule
Original Consent Form	Prior to registration
On-Study Form	Prior to starting treatment
Treatment Form	Every cycle
Toxicity Form	Continuous
Treatment Summary Form	Completion of treatment
Follow Up Form	Every 3 months for up to 5 years
Tumor Measurement Form	Baseline, end of every even numbered cycles, EOT, and for all standard of care disease assessments done during follow up until documented progression.
Echocardiogram & Holter Monitor Form	Baseline, and Day 1 of every odd-numbered cycle starting with Cycle 3
hscTNI & Galectin-3 Form	Day 1 of every cycle
BNP Form	Baseline and Day 1 of every odd-numbered cycle starting with Cycle 5

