## 12.0 MEASUREMENT OF EFFECT

### 12.1 Antitumor Effect – Solid Tumors

For the purposes of this study, patients should be re-evaluated for response every 6 weeks. In addition to a baseline scan, confirmatory scans should also be obtained not less than 4 weeks following initial documentation of objective response.

Response and progression will be evaluated in this study using the new international criteria proposed by the revised Response Evaluation Criteria in Solid Tumors (RECIST) guideline (version 1.1) [Eur J Ca 45:228-247, 2009]. Changes in the largest diameter (unidimensional measurement) of the tumor lesions and the shortest diameter in the case of malignant lymph nodes are used in the RECIST criteria.

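### On-treatment CT is timed by cycle in 10.1 and 11.0 but by calendar week in 12.1, and nothing says which rule governs after a delayed cycle, so delays can modestly lengthen recorded PFS

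*Combined protocol and SAP*

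**What the plan says.** Three places set the timing of on-treatment tumor imaging.

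- The calendar in 10.1 marks CT under "End of Each Even-Numbered Cycle" and again at end of treatment. The echocardiogram carries a 3-day window by footnote; the on-treatment CT has none. Section 10.2 uses the same columns for the control cohort.
- The form schedule in 11.0 matches the calendar: "Baseline, end of every even numbered cycles, EOT", then standard-of-care assessments in follow-up.
- Section 12.1 counts in calendar time: "patients should be re-evaluated for response every 6 weeks".

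Cycle length is not fixed. Section 5.1 says that doxorubicin is "typically given on Day 1 of a 21-day cycle" and that "the administration is not dictated per protocol". Section 5.4 foresees interruptions, since it opens its treatment-duration rule with "In the absence of treatment delays due to adverse events". After removal for reasons other than progression, 10.1 relies on imaging "until standard of care imaging shows progression per RECIST 1.1".

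The primary endpoint is PFS, tested only in the dexrazoxane cohort (14.1) against a historic median of 4.6 months with a bound of 3.7 months (14.3.1).

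**The concern.** Two cycles of 21 days make 6 weeks, so the rules agree for a patient treated on time. Once a cycle slips they diverge: by the calendar the CT moves with the cycle, and by 12.1 it does not. No section ranks one above the other. A site is likely to work from the calendar and the form, so the cycle rule is the one more likely to be followed.

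Progression is dated by the scan that shows it. Patients whose cycles are delayed would then be scanned later and have progression dated later. In a randomized comparison much of this could cancel between arms. Here the comparator is a fixed number, and the margin is 0.9 month (about 3.9 weeks), which is shorter than one 6-week scan interval.

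**Working it through.** **Inputs from the documents.** Historic median 4.6 months, bound 3.7 months, one-sided alpha 0.05, 57 patients (14.3.1); scan interval 6 weeks (12.1); cycle length 21 days (5.1). Margin: 4.6 − 3.7 = 0.9 month, and 0.9/4.6 = 19.6%, which matches the stated 20%.

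**The plan's power figure.** 14.3.1 states power 0.80 with 57 patients. A one-sample log-rank with 57 events gives √57 × ln(4.6/3.7) − 1.645 = 1.644 − 1.645 ≈ 0, so power of about 0.50. The 0.80 does not reproduce this way. A figure in that section is not shown and may hold further inputs. This is a separate matter and is not used below.

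**Scan dates** (weeks × 7/30.4375 = months):

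| Delay per two-cycle block | Scan weeks | Third scan |
|---|---|---|
| none | 6, 12, 18 | 4.14 months |
| 1 week | 7, 14, 21 | 4.83 months |
| 2 weeks | 8, 16, 24 | 5.52 months |

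**Simulation.** Assumptions: exponential PFS with true median 3.7 months (exactly at the bound), 57 events, each dated at the next scan. Deaths and end-of-treatment scans are not modeled. Delay rates are assumed, because the documents give none. The one-sample log-rank uses E = Σ(ln 2/3.7)·tᵢ and z = (57 − E)/√E, and declares non-inferiority if z < −1.645. In the calibrated version the cutoff on total exposure is set so that strict 6-week scanning gives an error of 0.050.

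| Scenario | Rise in mean recorded PFS (months) | Error, calibrated |
|---|---|---|
| strict 6-week scans | reference | 0.050 |
| 1-week delay in 10% of first six cycles | 0.02 | 0.052 |
| same, 25% | 0.04 | 0.055 |
| same, 50% | 0.08 | 0.060 |
| same, 100% | 0.16 | 0.072 |
| 2-week delay in 25% of first six cycles | 0.09 | 0.061 |
| 1-week delay in every cycle for as long as scanned | 0.25 | 0.090 |

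Without calibration the log-rank passes about 0.20 of trials on strict 6-week scans and 0.21 to 0.23 with 1-week delays in 10% to 50% of six cycles, a rise of about 1 to 4 points. The upper-end case is every patient scanned at uniform 7- or 8-week intervals throughout: about 0.26 and 0.31–0.32, or +6 and +11 to 12 points.

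The 0.20 starting level is not due to delays. True mean PFS is 3.7/ln 2 = 5.34 months, while scan-dated mean PFS on the 6-week grid is about 6.05, because progression is always recorded at the next scan.

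**Benchmark on a 6-week scan scale.** If 3.7 months is read as already scan-dated (true median about 3.2), the log-rank passes about 0.02, 0.03 and 0.05 of trials at uniform 6-, 7- and 8-week scans.

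**Kaplan-Meier interval (14.2).** Here the direction is not uniform. The lower limit for the median clears 3.7 only if survival at the last scan before 3.7 months is convincingly above 0.5. That scan falls at week 12, 14 or 16 (2.76, 3.22 or 3.68 months), where true survival is 0.5^(2.76/3.7) = 0.596, 0.5^(3.22/3.7) = 0.547 and 0.5^(3.68/3.7) = 0.502. Simulated chances that the lower 95% limit exceeds 3.7 are about 0.34, 0.12 and 0.03.

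**The case against.** The strongest reply is that 12.1 already sets a calendar interval, that all three sections agree for on-time treatment, and that only a precedence rule is missing. That is correct as to the text, and it rules out the reading that the plan chose cycles in place of calendar weeks. It does not settle what a site does after a delay, because the calendar and the form both say otherwise.

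A reader might also infer that every delay shifts the primary test. The documents do not support that. Deaths keep their own date, an end-of-treatment CT can date progression, delays after recorded progression have no effect, and imaging after removal from treatment follows standard of care instead of cycles.

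A third tempting reading takes the third scan's move from 4.14 to 4.83 months (0.69 month, 77% of the margin) as the shift in the endpoint. It is the displacement of one scan date for a patient delayed in three successive blocks. Mean recorded PFS moves only about 0.14 month (0.14/0.9, about 15% of the margin) even if every patient is scanned at 7-week intervals. Nor can the 0.20 pass rate be charged to this issue, since it is present under strict 6-week scanning and the fix leaves it there. Finally, on a 6-week-scale benchmark the pass rate stays at or near 0.05 even in the 8-week case. These points limit the size; they do not remove the conflict.

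**Conclusion.** The point stands as an unreconciled conflict between 10.1 and 11.0 on one side and 12.1 on the other, which takes effect whenever a cycle is delayed. Followed as written, the calendar lets treatment delays postpone the scan that dates progression, in a single-cohort test where nothing offsets it. Under the log-rank test of 14.3.1 this leans toward non-inferiority. Under the Kaplan-Meier interval of 14.2 the result moves with the scan dates and can go the other way.

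The size is modest at plausible delay rates: about 0.02 to 0.08 month in mean recorded PFS, and 0.2 to 1 percentage point of calibrated error (1 to 4 points uncalibrated). Uniform 7- or 8-week scanning is an upper-end case. All of this assumes exponential PFS, progression dated only at scheduled scans, and delay rates that the documents do not supply.

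A reader might infer a known net bias against 4.6 months. The documents do not allow that conclusion, because they do not give the historic trial's scan schedule or its delays. The correction is still worth making: it is cheap and concerns the dating of the primary endpoint.

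**What to change.** In 10.1 and 11.0, replace the cycle-based CT timing with the rule of 12.1: every 6 weeks from start of treatment (weeks 6, 12, 18, 24 and so on), with a stated window such as ±7 days, regardless of cycle number or dose delay. State the same start point and window in 12.1. Change 10.2 to match for consistency only, since the control cohort is outside the primary test.

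The cost is a short amendment to the calendar and form wording. Patients treated on time have the same scans. In patients with long delays a scan may no longer coincide with a cycle visit, or one extra scan may be needed. No dose or treatment rule changes.

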## 10.2 CONTROL ARM

Baseline/screening procedures may take place up to 14 days prior to the start of treatment, except consent and scans (including the echocardiogram and Holter monitor), which may take place up to 28 days prior to the start of treatment.

	Baseline / Screening	Day 1 of Each Cycle	Day 1 of Each Odd-Numbered Cycle	End of Each Even-Numbered Cycle	EOT	F/U
Informed consent	X					
H&P, ECOG PS	X				X	X
CBC	X					
CMP	X					
β-hCG 	X					
2D and 3D echocardiogram	X		X 			
CT C/A/P	X			X	X	
Dexrazoxane 		Given as SOC at cycle 5 or a cumulative dose of 350 mg/m 				
Blood for hscTnI and galectin-3	X	X 				
Blood for BNP 	X	After cumulative dose of 300 mg/m  of doxorubicin, and then every 6 weeks thereafter				
24-hour Holter monitor	X		X			
AE assessment	X	----- X				

1. Women of childbearing potential only
2. Can be drawn with a BMP or CMP if being drawn for routine pre-doxorubicin labs
3. Every 3 months for up to 5 years. Patients who are removed for reasons other than progression will be followed until standard of care imaging shows progression per RECIST 1.1.
4. No more than 30 minutes before SOC doxorubicin
5. With SOC pre-treatment bloodwork and 4 hours post-doxorubicin up until cycle 6
6. Except Cycle 1
7. -3 day window to allow for the echo to be read prior to the start of the next cycle

## 11.0 DATA SUBMISSION SCHEDULE

Case report forms with appropriate source documentation will be completed according to the schedule listed in this section.

Case Report Form	Submission Schedule
Original Consent Form	Prior to registration
On-Study Form	Prior to starting treatment
Treatment Form	Every cycle
Toxicity Form	Continuous
Treatment Summary Form	Completion of treatment
Follow Up Form	Every 3 months for up to 5 years
Tumor Measurement Form	Baseline, end of every even numbered cycles, EOT, and for all standard of care disease assessments done during follow up until documented progression.
Echocardiogram & Holter Monitor Form	Baseline, and Day 1 of every odd-numbered cycle starting with Cycle 3
hscTNI & Galectin-3 Form	Day 1 of every cycle
BNP Form	Baseline and Day 1 of every odd-numbered cycle starting with Cycle 5

## 12.0 MEASUREMENT OF EFFECT

### 12.1 Antitumor Effect – Solid Tumors

For the purposes of this study, patients should be re-evaluated for response every 6 weeks. In addition to a baseline scan, confirmatory scans should also be obtained not less than 4 weeks following initial documentation of objective response.

Response and progression will be evaluated in this study using the new international criteria proposed by the revised Response Evaluation Criteria in Solid Tumors (RECIST) guideline (version 1.1) [Eur J Ca 45:228-247, 2009]. Changes in the largest diameter (unidimensional measurement) of the tumor lesions and the shortest diameter in the case of malignant lymph nodes are used in the RECIST criteria.

